3. PROCEDURE

Screening and Selection of Subjects

Patients visiting the Department of Dentistry at Brescia University will be asked to participate in this study. Subjects will report to the clinical facility and be screened by the dental examiner to identify those subjects who meet the inclusion/exclusion characteristics. The findings of this initial screening procedure will be recorded on the CRF. Subjects who meet the

inclusion/exclusion characteristics and sign an Informed Consent Form will be entered into the study.

Baseline Oral Soft and Hard Tissue Assessment

All subjects will receive an evaluation of their oral soft and hard tissues. This examination will include an evaluation of the soft and hard palate, gingival mucosa, buccal mucosa, muco gingival fold areas, tongue, sublingual and submandibular areas and the tonsillar and pharyngeal areas. The results of this evaluation will be recorded on the CRF.

Clinical Periodontal Evaluation

All patients receiving treatment will be evaluated by the dental examiner for the following assessments (see Study Flow Chart):

- Collection of subgingival plaque samples;
- Full Mouth Plaque Score (PI);
- Periodontal Inflammation (BOP);
- Probing Pocket Depth (PD);
- Recession (REC);
- Clinical Attachment Level (CAL).

Clinical attachment level (CAL) is the measurement of the position of the soft tissue in relation to the cemento-enamel junction (CEJ) that is a fixed point that does not change throughout life. All parameters will be recorded in the CRF.

Treatment

Patients who have been identified for treatment receive a GBT session and after OHI will be randomized according to a randomization table generated.

Follow up

Following completion of GBT and OHI the subject will be given the appropriate number of interproximal cleaning devices and discuss with the operator about the appropriated toothbrush and toothpaste for home use. Subjects will be asked to refrain from using any other adjunctive oral home care products during the study period. Every necessary study lozenges will be given to all patients to consume at home. The patients will be instructed to dissolve these on their tongue twice a day, preferably after brushing, for 3 weeks.

After 3 weeks the compliance will be recorded and microbiological sample will be collected again. At 3 and 6 months the following assessments (see Study Flow Chart) will be recorded:

- Collection of subgingival plaque samples;
- Full Mouth Plaque Score (PI);
- Periodontal Inflammation (BOP);
- Probing Pocket Depth (PD);
- Recession (REC);
- Clinical Attachment Level (CAL).

Study Flow Chart

Study phase	Enrolment	Treatment	Follow-up	Follow-up	Follow-up
Study visit	Visit 1	Visit 2 (T0)	Visit 3 (T1)	Visit 4 (T2)	Visit 5 (T3)
Study Week	-29 days	0	3 weeks	3 months	6 months
Selection criteria	+				
Informed consent	+				
Demographics, ethnics	+				
General health status	+	+	+	+	+
Medical & dental history	+				
Concomitant therapy/treatment	+	+	+	+	+
Safety (adverse events and serious adverse events)		+	+	+	+
Data collection (PD,REC, BOP, PI)	+			+	+
Microbiological Sample		+	+	+	+
Randomisation		+			
GBT		+			+
OHI		+	+	+	+
Dispensing standard interdental floss		+			
Dispensing study lozenges		+			

4. STATISTICAL ANALYSIS

Sample size determination

The sample size was calculated via simulation assuming an expected difference of 1mm pocket probing depth and using a linear mixed effect model considering patients as random effects. We simulated 1000 realizations of pocket probing depth applying the data correlation structure from the AgPro study (fixed effect correlation = -0.664; random effects intercept SD = 0.974; random effects residual SD = 1.65) and assuming an average of 7 experimental sites per patient. A sample size of 20 patients per group allowed for a power of at least 80% at the chosen $\alpha = 0.05$. Taking into account a dropout rate of 10%, we estimated a total sample size of 44 patients. The simulation was performed using R (version 3.6.1).

Statistical Analysis

Data will be described using standard summary statistics such as mean and standard deviations for quantitative variables and proportions for categorical variables. The primary outcome is pocket probing depth (PPD). Only the sites with PPD greater or equal to 6mm at baseline were considered or PPD equal to 5mm and BoP+. For the primary outcome a linear mixed effect model will be used considering patients as random effects.

Secondary continuous outcomes will be modelled using a linear mixed model while generalized mixed models will be applied to categorical outcomes. Data will be modelled both using a 1-level hierarchical model (clustering level: patient) after averaging the outcome variables within subject, and using a 3-level (patient, tooth and site) hierarchical model. Results will be expressed as estimates and relative 95% confidence intervals. A significant level of 5% will be used for all the comparisons and all analysis will be performed using R (version 3.6.1 or higher).

Evaluation of Safety

The following safety variables will be used for the evaluation of safety:

- Adverse events (AE);
- Adverse reactions (AR).

The total number of AEs and the total number of AEs at least possibly related to the study treatment, as well as the total number of patients affected by at least one adverse event will be calculated per treatment group.

The type of AE classified by organ system (according to MedDRA terminology) will be tabulated. Serious and/or unanticipated adverse events and AEs resulting in discontinuation or reduction/withdrawal of the study treatment will be presented separately.

Safety analysis set

Safety summaries will be based on the safety analysis set which will consist of all patients who received the test/control treatment.

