Total Sample Size:	44 adult subjects will be recruited (randomized) to participate in this study, with 40 expected to complete the study.
Primary Efficacy Variable:	Primary outcome measure will be the changing of PD in millimeters.

Clinical and microbiological efficacy of *Lactobacillus reuteri* in the supportive therapy of periodontitis: a 6 months Randomized Controlled Trial study.
PROTOCOL #PERIOPRO

Protocol Date: JAN 13, 2020

Protocol Approval

Signature Page

[name]
University-Hospital of Brescia, Italy

Date

ADDRESSES AND RESPONSIBILITIES

Addresses

Study Centres:	Section of Periodontics, School of Dentistry, Department of Surgical Specialities, Radiological Science and Public Health University of Brescia [name]
	[name] (Principal Investigator) [contact] Email: [contact]
Study coordinator:	[name] Section of Periodontics, School of Dentistry, Department of Surgical Specialities, Radiological Science and Public Health University-Hospital of Brescia Brescia, IT
Data Management & Monitoring:	[name] Section of Periodontics, School of Dentistry, Department of Surgical Specialities, Radiological Science and Public Health University-Hospital of Brescia Brescia, IT
Statistician:	[name] Unit of Biostatistics and Bioinformatics, Department of Molecular and Translational Medicine University of Brescia Brescia, IT
Microbiologist:	[name] Head of the Department of Preventive Dentistry Professor in Oral Microbial Ecology Academic Centre for Dentistry Amsterdam Vrije Universiteit Amsterdam and University of Amsterdam Amsterdam, the Netherlands

Responsibilities

The **principal investigator's** responsibilities are described in detail in ISO norm 14155:2011 for the clinical investigation of medical devices for human subjects.

The role of the principal investigator is to implement and manage the day-to-day conduct of the clinical investigation as well as ensure data integrity and the rights, safety and well-being of the subjects involved in the clinical investigation.

The principal investigator shall be qualified by education, training and experience to assume responsibilities for the proper conduct of the clinical investigation. In particular, the principal investigator is responsible for:

- qualification of investigation site;
- communication with Ethics Committee;
- compliance with Informed Consent process;
- compliance with Clinical Investigation Plan.

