Under the direct supervision of the Principal Investigator, certain duties may be delegated during the course of the study. These responsibilities will be documented on the transfer of responsibilities form maintained in the Investigator Site file.

The **Statistician** will be responsible for:

- sample size calculation;
- statistical plan;
- statistical section of the protocol;
- statistical evaluation;
- final statistical report.

The **Microbiologist** will be responsible for:

- sample microbiological processing and analysis;
- final microbiological report.

OBJECTIVE

The study will be performed to assess the efficacy of the addition of *Lactobacillus reuteri* containing lozenges in the supportive therapy of periodontitis in terms of reduction of PD (Probing Depth).

INTRODUCTION

Probiotics are defined as 'live microorganisms which, when administered in adequate amounts, confer a health benefit on the host'. The influence of probiotics on pathogens flora can derive from three principal modes of action: innate and acquired host defense modulation, production of antibacterial substances and competitive exclusion mechanism. In particular, *Lactobacillus reuteri* has been studied for its antibacterial and anti-inflammatory properties.

It is a heterofermentative bacterium and the distinct strains have different characteristics. In particular it acts as an antibiotic, induces oxidative stress on pathogens, is resistant to proteolytic and lipolytic and present anti-inflammatory properties.

Literature pointed out to potential effectiveness of *L. reuteri* as an adjunct to non-surgical periodontal therapy in initial treatment of periodontitis patients but underlined the limits of their conclusions due to the heterogeneity of the studies and to the few patients included. There is thus a need for more long-term randomized controlled studies. In particular, only one study addressed the use of this probiotic during the supportive therapy and in particular in patients with severe forms of periodontitis but few patients were included.

Patients meeting the criteria of periodontitis stage III and IV, grade C are considered to be affected by severe and advanced forms of periodontitis with a rapid rate of progression. This group of patients could particularly benefit from supplements in the maintenance of periodontal health.

STUDY OUTCOMES

- a. Primary outcome measure: change in PD
- b. Secondary outcomes:

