1. STUDY DESIGN

The study design was chosen according to the current standards required by ISO, GCP and according to national requirements.

- a. A Parallel-Arm, Statistician, Operator and Examiner are blinded, RCT will be established;
- b. The RCT will be run as mono-center;
- c. A total of 44 subjects will be recruited to participate in the study. It is expected that all of 40 subjects will complete the study in total;
- d. Admission into the study will be via rolling admission (estimated recruitment time: 12 months);
- e. Each subject must have at least 2 residual sites/pockets with probing depth ≥ 6 mm or pockets of 5 mm with bleeding on probing in two different quadrants;
- f. Each subject will follow the following treatment protocol:
 - i. – Visit 1 (Screening): (within 29 days prior to baseline) – consent secured; screening and entry into study; baseline data collection; full periodontal charting (full-mouth PD, REC, BOP, PI); identification the sites for microbiological sample.
 - ii. – Visit 2 (T0 – Baseline Visit+Treatment): collection of microbiological samples from the two deepest sites in two different quadrants. All patients receive a full mouth periodontal treatment (GBT) and OHI (oral hygiene instruction). According to the list of randomization the patient will be allocated into one of the two arm of probiotic treatment: study lozenges are given to all patients to consume at home. The patients are instructed to dissolve these on their tongue twice a day, preferably after brushing, for 3 weeks. The patients of the probiotic group will receive probiotic lozenges containing *Lactobacillus reuteri* DSM 17938 and *Lactobacillus reuteri* ATCC PTA 5289 (a minimum of 2×10^8 colony-forming units L. reuteri Prodentis/lozenge, BioGaia AB). The patients of the control group will receive control lozenges without live bacteria. Furthermore, the probiotic and control lozenges will be identical in taste, texture and appearance.
 - iii. – Visit 3 (T1) – 3 weeks: the participants will be asked to return the empty packages of the study medication to examine the adherence. At that time, side effects will also be questioned by the examiner by means of an open question. Collection of the

microbiological sample will be performed from the same subgingival sites as during Baseline (T0) and reinforcement of OHI.

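### The primary PD analysis fixes neither the visit, nor the fixed effects, nor change versus level, and uses baseline PPD only to select sites; one baseline-adjusted 6-month model would settle it almost free

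*Combined protocol and SAP*

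**What the plan says.** **Form of the outcome.** The synopsis states "Primary outcome measure will be the changing of PD in millimeters", and the Study Outcomes section states "Primary outcome measure: change in PD". Section 4 (Statistical Analysis) states "The primary outcome is pocket probing depth (PPD". Section 3 lists "Probing Pocket Depth (PD" among the assessments, so PD and PPD are one measurement. What differs is change versus level.

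**Model.** The specification is "For the primary outcome a linear mixed effect model will be used considering patients as random effects". Treatment, time, treatment-by-time and baseline terms are not mentioned. A later sentence in section 4 announces both a patient-averaged 1-level fit and a 3-level fit. It follows the sentence on secondary outcomes and does not say whether it also covers the primary.

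**Visit.** The Study Flow Chart has PD charted at Visit 1, T2 (3 months) and T3 (6 months). Six months appears in the title, as the participation period and as the last visit, but nowhere as the time of the primary comparison. The 1 mm planning difference has no visit attached either.

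**Baseline.** Section 1 collects at Visit 1 "baseline data collection; full periodontal charting (full-mouth PD, REC, BOP, PI". The analysis text uses this only to select sites: "Only the sites with PPD greater or equal to 6mm at baseline were considered or PPD equal to 5mm and BoP" positive.

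**The concern.** The plan allows several different primary tests: level or change, 3 or 6 months or both, with or without baseline. They need not agree, and their power can differ a good deal. A reader cannot tell which one the 1 mm difference and the SDs were meant for. The choice could still be made after the data are seen.

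The trial has about 40 analysable patients and little power to spare. Its plan does not use a covariate that is already recorded for every eligible site and could sharpen the treatment comparison.

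**Working it through.** **Inputs from section 4 (sample size):** 20 patients per group; difference 1 mm; between-patient SD 0.974; residual SD 1.65; 7 sites per patient; 5% level.

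**Assumptions, not in the documents:** the test is two-sided; the SDs describe follow-up PPD; r is the correlation between patient-mean Visit 1 PD and patient-mean follow-up PD. If the SDs describe change instead, the unadjusted figure in step 1 belongs to the change analysis.

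**1. The plan's own figure.** The variance of a patient mean is 0.974² + 1.65²/7 = 0.9487 + 0.3889 = 1.3376 (SD 1.157). The SE of the difference is √(2 × 1.3376/20) = 0.366 mm, and 1/0.366 = 2.73.
- Normal approximation: power 78.1%.
- Noncentral t, 38 df: 75.9%.
- Simulated random-intercept model, maximum-likelihood Wald test: 79.3%.

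The plan states at least 80% from 1000 simulations, whose Monte Carlo SE is √(0.8 × 0.2/1000) = 1.3 points. The stated figure is therefore reproduced approximately. The exact value depends on the test used. The t-based value is the reference below.

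**2. Unadjusted change score, equal baseline and follow-up SDs.** Variance = 2 × 1.3376 × (1 − r), 38 df.

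**3. Adjustment for patient-mean baseline PD.** Variance = 1.3376 × (1 − r²) × (1 + 1/36), 37 df. The factor 1 + 1/36 is the expected cost of chance baseline imbalance with 40 patients. Equivalent patients per group = 20/[(1 − r²) × 37/36].

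| r | Level, unadjusted | Change, unadjusted | Baseline-adjusted | Equivalent n per group |
|---|---|---|---|---|
| 0 | 75.9% | 47.0% | 74.7% | 19.5 |
| 0.1 | 75.9% | 51.1% | 75.2% | 19.7 |
| 0.2 | 75.9% | 55.8% | 76.4% | 20.3 |
| 0.3 | 75.9% | 61.5% | 78.6% | 21.4 |
| 0.5 | 75.9% | 75.9% | 85.8% | 25.9 |
| 0.7 | 75.9% | 93.0% | 95.7% | 38.2 |

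Example at r = 0.5: 1.3376 × 0.75 × 37/36 = 1.031, SE = √(2 × 1.031/20) = 0.321 mm.

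**4. Unequal SDs.** Selecting sites by depth may narrow the baseline spread. If the baseline SD is half the follow-up SD and r = 0.5, the change-score variance is 1.3376 × (1 + 0.25 − 0.5) = 1.003 and power is 86.8%, against 85.8% with adjustment. Adjustment is therefore not best in every case; here it falls about 1 point short.

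**5. Why adjustment reconciles change and level.** Let site baseline PD be a fixed effect. Replacing PD by PD minus baseline then lowers the baseline coefficient by exactly 1 and leaves the residuals unchanged. The variance components, treatment estimate and SE are the same either way. The patient-mean term has a separate purpose: 0.9487/1.3376 = 71% of the patient-mean variance lies between patients, and the gains in step 3 are computed for that term.

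**The case against.** **Change and level need not conflict.** In a repeated-measures model that includes the baseline visit, change is the treatment-by-time contrast. That stands, and it rules out calling the two wordings a contradiction. But the plan does not specify that model.

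**Six months is obvious.** It is the natural reading of the title and final visit, but the primary comparison is not tied to it.

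**Adjustment is a preference.** This stands in part. An unadjusted randomised comparison is valid, and at r = 0 or 0.1 adjustment loses up to about 1 point. Restricting analysis to sites of 5 mm or deeper may keep r low, so a large gain should not be promised.

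**Adjustment alone does not leave one model.** This also stands. The sentence announcing 1-level and 3-level fits could be read to cover the primary outcome, so the plan must say which model is primary.

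The documents do not support two stronger readings that a reader might infer:
- *Inflated type I error from testing both visits.* Error would exceed 5% if significance at either visit could count, but the plan states no such rule. The blinded statistician and the blind data review also limit choice by direction of effect, though not by p-value.
- *The planning model had no baseline term, because section 4 quotes "fixed effect correlation = -0.664".* That value is attributed to another study whose fixed effects are not named. One correlation does not identify them.

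**Conclusion.** The point holds as a gap in specification and a nearly free improvement, not as a correction of an invalid analysis. The primary visit, the fixed effects and the form of the outcome are all open, and no other section supplies them.

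The firm benefit is one estimand and one test. The gain in precision is conditional. Relative to 75.9% unadjusted, adjusted power runs from 74.7% at r = 0 to 85.8% at r = 0.5, equivalent to about 19.5 to 26 patients per group. Below r of about 0.2 there is essentially no gain. Leaving the form open matters more: an unadjusted change score could be much worse or clearly better than the level. All these figures rest on an assumed r, on the SDs describing follow-up PPD, and on a two-sided t-based test. The sponsor should act on this.

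**What to change.** In the synopsis, the Study Outcomes section and section 4, state the same single primary analysis:

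- Outcome: PD at T3 (6 months), at sites that qualify at baseline.
- Model: the linear mixed model with patient random effects already named, with treatment, site-level Visit 1 PD and patient-mean Visit 1 PD as fixed effects. Both baseline terms are required; neither is optional.
- Test: once, two-sided 5%.
- T2 (3 months): supportive.
- This is the only primary model; the 1-level and 3-level fits are secondary or sensitivity analyses.
- Baseline means the Visit 1 charting, which may precede T0 by up to 29 days.

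The cost is a few lines of text, submitted as an amendment under section 9 if the protocol is already approved, and one or two degrees of freedom. If baseline proves uninformative, at most about 1 point of power is lost per covariate. No patients, visits or measurements are added.

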AEs include any clinically significant deterioration of a subject's medical status, after being enrolled and signing an informed consent form. The AE may involve any organs or systems and can be represented by the new onset or the deterioration of a disease, a syndrome, a symptom, a physical sign, as well as by findings and results of instrumental examinations and laboratory tests. Any medically relevant and untoward change from baseline, including frequency or pattern changes for a fluctuating condition (e.g., migraine), occurring after the administration of investigated treatments

is an adverse event. All such occurrences must be recorded and reported accordingly, whether they appear causally related to the study medication, or not.

Serious Adverse Device Effect (SADE) is an adverse device effect that has resulted in any of the consequences characteristic of a serious adverse event.

Unanticipated Serious Adverse Device Effect (USADE) is a serious adverse device effect which by its nature, incidence, severity or outcome has not been identified in the current version of the risk analysis report or investigator's brochure (IB).

NOTE: Anticipated SADE (ASADE): an effect which by its nature, incidence, severity or outcome has been previously identified in the risk analysis report or IB.

The following events are considered reportable:

- any SAE;
- any Device Deficiency that might have led to a SAE if:
 - a) suitable action had not been taken or
 - b) intervention had not been made or
 - c) if circumstances had been less fortunate;
- new findings/updates in relation to already reported events.

Reportable events have to be reported by clinical investigators.

Assessment of Causality

The following criteria are to be used for the assessment of the causal relationship to the test/control treatment. For classification, all criteria of one of the following categories must be met:

related, if

- a timely correlation exists and
- dechallenge and/or rechallenge and
- a biological plausibility exists and
- other factors are clearly excluded
- a medical report or clinical proof exists;

possibly related, if

- a timely correlation exists and
- dechallenge and/or rechallenge and
- a biological plausibility exists and
- a medical report or clinical proof does not exist;

unrelated, if

- a timely correlation does not exist or is uncertain and
- dechallenge and/or rechallenge does not exist and
- a biological plausibility exists and

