- a medical report or a clinical proof does not exist;

unknown, if

- not enough information exists for evaluation
- no further contact with reporter possible.

Sound medical/clinical judgment will be applied when assessing the causality and seriousness of the adverse events.

Adverse Event Reporting

The study center will provide the study participants with emergency telephone numbers for study related support and feedback. The emergency telephone number is operated by either an investigator of the study or by a qualified person designated by the principal investigator. The schedule of reachability of the emergency telephone number will be defined prior to start of the study.

Serious Adverse Events

The Investigator shall immediately after awareness (and in any event, not later than within 24 hours after awareness) inform the PI. The Investigator will send the SAE report to the following email address: [contact]. Appendix 3 has to be used for SAE reporting. Form has to be completed electronically and in English.

Adverse Events

Adverse events will be assessed by the investigator or designee within 24 hours for severity, relationship to the study product, possible etiologies, and whether the event meets the criteria as a

serious adverse event and therefore requires immediate notification to the PI. For data collection purposes, the outcome of all adverse events recorded on the Adverse Reaction section of the CRF will be designated as of the completion of the final evaluation or examination. However, the investigator is responsible for following all adverse events until resolution or until no longer of clinical concern, and providing these data to the PI. At the end of the study, the investigator will report all adverse events (serious and non-serious) to the PI on CRFs. Forms have to be completed electronically and in English.

Pregnancy

No pregnant women (according to medical history) will intentionally be enrolled in this study. In the event a woman enrolled in this clinical research study becomes pregnant during the course of the study, participation in this study will be terminated upon the clinical staff's notification of the event. The subject's medical records used in this study will be updated to reflect the pregnancy and there will be follow-up contact until the end of the pregnancy to record the outcome in the clinical file.

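### Treatment-related adverse events are to be counted only as events, so the planned totals cannot show how many patients were affected, and events of unknown causality have no stated place in that figure

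*Combined protocol and SAP*

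**What the plan says.** Section 4 (Evaluation of Safety) sets out three totals: all AEs, "the total number of AEs at least possibly related to the study treatment", and, for patients, "the total number of patients affected by at least one adverse event will be calculated per treatment group". The patient count carries no causality restriction. The section also plans a MedDRA organ-system table and a separate presentation of serious or unanticipated AEs and of AEs leading to discontinuation, reduction or withdrawal of treatment. It does not say whether those tables count events or patients. The safety set is "all patients who received the test/control treatment".

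Section 8 (Assessment of Causality) has four classes: related, possibly related, unrelated and unknown. The governing rule is "For classification, all criteria of one of the following categories must be met". The *unknown* class lists two conditions: "not enough information exists for evaluation" and "no further contact with reporter possible". Neither section says where an *unknown* AE goes in the related total, or how repeat episodes in one patient are counted.

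**The concern.** Patients are randomised, not events. In an arm of about 22, the question a reader brings to the safety table is how many people had harm that may be due to the lozenge. The plan answers that only for AEs of any cause. For possibly related AEs it gives a number of events, and one patient with a recurring complaint can create, enlarge or mask a difference between arms without the totals showing it.

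The second gap concerns classification. A threshold of at least possibly related takes in the first two classes only. An *unknown* AE then counts, for this figure, like an unrelated one. Leaving it out can lower the related total but cannot raise it.

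**Working it through.** **No plan figure to reproduce.** The documents give no AE rate, no number of repeats per patient and no share of *unknown* AEs. Part 1 uses invented totals to make a logical point. The rates in parts 2 and 3 are assumptions.

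**1. What the planned totals can and cannot show.** For one arm, let T be all AEs, E the AEs at least possibly related, and P the patients with any AE. The number of patients with a related AE, R, is limited only by

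- upper limit: R ≤ min(E, P);
- lower limit: R ≥ max(1, P − (T − E)) when E ≥ 1, because at most T − E patients can have only other AEs.

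Illustration: T = 14, E = 6, P = 8. The upper limit is min(6, 8) = 6. The lower limit is max(1, 8 − 8) = 1. The same three totals fit six patients with one related event each, or one patient with six.

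**2. How far event totals can drift when the arms are truly equal.**

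Inputs: 22 patients per arm (44/2, from the sample size; equal allocation assumed). Assumed: probability p that a patient has a related complaint, the same in both arms, and a distribution w of events per affected patient. Each patient contributes 0 events with probability 1 − p, and j events with probability p·w(j). The arm total is the sum over 22 independent patients. The result is the probability that the two arm totals differ by 5 or more.

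- *At most two events:* 10% to 50% of affected patients have a second event.
- *Up to four events:* 1, 2, 3 or 4 with probabilities 0.40, 0.25, 0.20, 0.15. The mean is 0.40 + 0.50 + 0.60 + 0.60 = 2.1, so at p = 0.15 the expected total is 22 × 0.15 × 2.1 = 6.9 events per arm.

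| Assumed risk, equal in both arms | Patients differ by ≥5 | Events differ by ≥5, at most two each | Events differ by ≥5, up to four each |
|---|---|---|---|
| 10% | 2% | 5–15% | 33% |
| 15% | 6% | 10–23% | 42% |

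If exactly the same number of patients is affected in both arms (p = 0.15), event totals still differ by 4 or more in 19% of trials with up to four events each, but in at most about 0.5% with at most two.

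A model with heavier repetition (geometric extra events, mean 2 per affected patient) and risks of 10–30% gives 33–56% for events against 2–14% for patients. The direction is the same throughout, and the size depends on how often patients repeat.

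**3. The *unknown* class.** Let r be the share of AEs rated related or possibly related, u the share rated *unknown*, and s the fraction of *unknown* AEs that are truly related. Taking the ratings of the other AEs as correct, the planned figure captures r / (r + u·s) of related AEs. With r = 0.30 (assumed):

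- u = 0.10, s = 0.5: 0.30 / 0.35 = 86%;
- u = 0.30, s = 0.5: 0.30 / 0.45 = 67%;
- u = 0 or s = 0: 100%.

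**The case against.** A reader might infer that the plan understates related harm. The documents do not support that as a fact. Understatement needs *unknown* AEs to occur and some of them to be truly related, and nothing in the text gives either number. The exclusion itself follows from the wording of the threshold and is not a stated rule. Section 8 also works against a large *unknown* class: relationship to the product is to be assessed within 24 hours, AEs are followed until resolved or no longer of clinical concern, and under the all-criteria rule both conditions of the class would have to hold. The planned 10% dropout says nothing about its size, since a patient who silently stops attending leaves an unreported AE, not one rated *unknown*. Nor are *unknown* AEs lost: they stay in the total AE count and the any-cause patient count.

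A reader might also infer an inflated false-positive rate. The safety section names no test for AEs and reads as descriptive, so a gap of 5 events triggers nothing. The risk is a misleading table, not a demonstrated type I error.

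Frequent repeats can be doubted too. Lozenges are handed out at T0 and taken for three weeks, so the T0 safety entry adds little and T2 and T3 fall well after the course. Both the related and possibly related classes also list "dechallenge and/or rechallenge and", which a complaint lasting months after stopping may not meet. This is why the at-most-two rows deserve as much weight as the 42%.

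Finally, CRFs carry the subject number, so the missing count could be produced later without a change of plan. That is true, but a count chosen after the data are seen is weaker than one written down now. None of these objections supplies a planned count of patients with a related AE.

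**Conclusion.** The point holds in a limited form. The plan counts related AEs as events and patients only for AEs of any cause, so its totals do not show how many randomised patients had harm at least possibly due to treatment. That follows from the text and needs no assumption. On its plain reading the related figure also omits *unknown* AEs, which can understate related harm but need not.

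Neither effect can be sized from the documents. With 22 per arm and equal assumed risk of 10–15%, a spurious gap of 5 or more related events arises in about 5–23% of trials with at most two events per affected patient, and in about 42% at 15% risk with up to four. The same gap in patients arises in about 2–6%. The efficacy analysis is untouched. This is a worthwhile reporting correction, not a threat to the trial's main conclusion.

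**What to change.** In section 4, Evaluation of Safety, add the following.

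- For AEs at least possibly related to treatment, for serious AEs and for each organ class, report per arm the number and percentage of safety-set patients with at least one event, beside the number of events. Base the descriptive comparison of the arms on the patient count.
- Show AEs of *unknown* causality on their own row, with a sensitivity count that adds them to the related AEs. Folding them into the headline related figure is not advised, since that would override the protocol's own four classes and could err in the other direction.
- Because event counts stay in the tables, say whether a complaint that continues across visits counts once or again at each visit.

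The cost is two or three sentences and a few table columns, from data already recorded on CRFs by subject number. The small downside is a sensitivity figure that may look slightly less favourable than the headline one. The wording should be settled before unblinding.
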